# 4.3 SAFETY FOLLOW-UP VISIT

Each subject should be followed for 30 days (+7) after his or her last dose of study drug (i.e., the "safety follow-up visit") to monitor for resolution or progression of AEs (see Section 6.2.7) and to document the occurrence of any new events, regardless of whether the subject receives a new anticancer therapy or demonstrates disease progression within this timeframe; after this period, investigators should report SAEs or other AEs of concern that are believed to be related to prior treatment with acalabrutinib (see Section 6.2.1). Subjects who withdraw consent for study treatment should still be encouraged to complete the safety follow-up assessments, but these assessments cannot be mandated if subject consent for further study participation is withdrawn. The Schedules of Assessments (Appendix 5 and Appendix 6) describe the procedures required for safety follow-up.

# 4.4 TIME-TO-NEXT TREATMENT AND SURVIVAL

Subjects who discontinue study therapy will continue to be followed for assessment of time-to-next therapy unless they withdraw consent for further follow-up. After discontinuing study therapy, subjects will also be contacted approximately every 12 weeks until death, withdrawal of consent by subject, loss to follow-up, or study termination by the sponsor, whichever comes first.

### 4.5 MISSED EVALUATIONS

Missed evaluations should be rescheduled and performed as close to the original scheduled date as possible. An exception is made when rescheduling becomes, in the investigator's opinion, medically unnecessary or unsafe because it is too close in time to the next scheduled evaluation. In that case, the missed evaluation should be abandoned.

# 5.0 STATISTICAL METHODS OF ANALYSIS

# 5.1 GENERAL CONSIDERATIONS

Descriptive statistics (including means, standard deviations, and medians for continuous variables and proportions and CIs for discrete variables) will be used to summarize data as appropriate. As appropriate, analyses will be performed by cancer type or overall. Depending on Part 1 and the number of expansion cohorts opened in Parts 2 and 3, a total of 6 to 324 evaluable subjects will be enrolled in this study. Under Amendment 4 of this protocol, the planned total enrollment was approximately 160 evaluable subjects; enrollment was closed in May 2017 with a total of 161 evaluable subjects.

### 5.2 SAMPLE SIZE JUSTIFICATION

In Part 1 (DLT review), enrollment of 6 subjects for DLT review is consistent with sample sizes used in oncology studies for determination of MTD. The trial employs the standard National Cancer Institute definition of MTD (dose associated with DLT in <33.3% of subjects). Provided ≤1 DLT occurs during the DLT review, then expansion will occur in Part 1 to include up to 24 subjects in a select group of histologies (as described in Section 3.0). The safety and preliminary efficacy results from Part 1 will be used to determine opening Part 2 and Part 3 of the protocol.

In Part 2 (expansion groups), enrollment of 30 subjects per group offers the opportunity to determine if there is sufficient antitumor activity to warrant further development in the selected tumor types. An ORR of  $\geq$ 20% is considered the minimum value of potential interest in each of

the selected indications. If <2 subjects per cohort experience an objective response, the probability is >0.90 that an ORR of  $\geq$ 20% will be excluded for that cancer. If 2 subjects in a group experience an objective response, the upper bound of a 1-sided exact binomial 90% CI=16.8%.

In Part 3, safety and response data will be reviewed after the initial 12 subjects have completed 24 weeks of treatment (i.e., the Week 25 visit) or have discontinued treatment before Week 25. The first 12 subjects will be evaluated regardless of the length of treatment with acalabrutinib alone or in combination with pembrolizumab. If <2 subjects who received acalabrutinib monotherapy or the combination with pembrolizumab have achieved a response of "clinical improvement" or better (see Table 9), the MF group will not be expanded. The decision to expand the study is multifactorial and needs to take into consideration the nature and quality of response, safety, and evolving competitive landscape. If the safety and response data indicate that further evaluation is warranted, up to 18 additional subjects with MF (for a total of up to 30 subjects) will be treated on the same adaptive regimen as was given to the first 12 subjects.

 Table 10 shows the 2-sided exact 90% binomial CIs on the true response rate for the range of
 all possible values for the observed response rate in the initial group of 12 subjects.

Beenenees n	Response Rate, %	90%CI	
Responses, n		Lower Bound	Upper Bound
0	0%	0%	22%
1	8%	0%	34%
2	17%	3%	44%
3	25%	7%	53%
4	33%	12%	61%
5	42%	18%	68%
6	50%	25%	75%
7	58%	32%	82%
8	67%	39%	88%
9	75%	47%	93%
10	83%	56%	97%
11	92%	66%	100%
12	100%	78%	100%

Table 10Two-Sided Exact 90% CIs for Response Rate in Initial Group in Part 3
(N=12)

CI=confidence interval.

If the MF group is expanded, enrollment of 30 subjects offers the opportunity to determine if there is sufficient antitumor activity to warrant further development in MF. A response rate

(clinical improvement, PR, or CR) of  $\geq$ 25% within the sample size of 30 subjects with MF is considered the minimum value of potential interest in this highly unmet medical need population of MF patients with thrombocytopenia or anemia. To reject the null hypothesis of response rate  $\leq$ 5% in favor of an alternative hypothesis that the response rate is  $\geq$ 25%, 30 subjects will preserve approximately 90% power to detect the difference at a 0.05 level of significance by 1-sided exact test for single proportion.

Considering the planned expansion cohort size of 30 subjects, Table 11 shows the 2-sided exact 90% binomial CIs on the true response rate for the range of all possible values for the observed response rate.

	Response Rate, %	90%CI	
Responses, n		Lower Bound	Upper Bound
0	0%	0%	10%
1	3%	0%	15%
2	7%	1%	20%
3	10%	3%	24%
4	13%	5%	28%
5	17%	7%	32%
6	20%	9%	36%
7	23%	11%	39%
8	27%	14%	43%
9	30%	17%	47%
10	33%	19%	50%
11	37%	22%	53%
12	40%	25%	57%
13	43%	28%	60%
14	47%	31%	63%
15	50%	34%	66%
16	53%	37%	69%
17	57%	40%	72%
18	60%	43%	75%
19	63%	47%	78%
20	67%	50%	81%
21	70%	53%	83%
22	73%	57%	86%
23	77%	61%	89%
24	80%	64%	91%
25	83%	68%	93%
26	87%	72%	95%
27	90%	76%	97%
28	93%	80%	99%
29	97%	85%	100%
30	100%	90%	100%

# Table 11Two-Sided Exact 90% Cls for Response Rate in Expansion Cohorts in
Part 2 and Part 3 (N=30)

CI=confidence interval.

# 5.3 DEFINITION OF ANALYSIS POPULATIONS

The following definitions will be used for the efficacy and safety analysis populations.

 All-treated population: All enrolled subjects who receive ≥1 dose of any study drug (either acalabrutinib or pembrolizumab). The safety analyses and primary efficacy analyses will be performed on the All-treated population.

- Efficacy-evaluable population: All subjects in the All-treated population who have ≥1 evaluable response assessment after the first dose of study drug (either acalabrutinib or pembrolizumab). Sensitivity analyses for efficacy will be carried out on the Efficacy-evaluable population.
- **PD** analysis **population**: A subset of subjects from the All-treated population who have sufficient baseline measurements and undergo ≥1 PD assessment after treatment. This analysis set will be used for PD parameters.

# 5.4 MISSING DATA HANDLING

No imputation of values for missing data will be performed except that missing or partial start and end dates for AEs and concomitant medication will be imputed according to prespecified, conservative imputation rules. Subjects lost to follow-up (or drop out) will be included in statistical analyses to the point of their last evaluation.

# 5.5 ENDPOINT DATA ANALYSIS

### 5.5.1 Safety Endpoint

Safety summaries will include summaries in the form of tables and listings. The frequency (number and percentage) of treatment-emergent AEs will be reported in each treatment group by MedDRA System Organ Class and Preferred Term. Summaries will also be presented by the severity of the AE (per CTCAE, v4.03 or higher) and by relationship to study drug (e.g., either acalabrutinib, pembrolizumab, or both).

Laboratory shift tables containing counts and percentages will be prepared by treatment assignment, laboratory parameter, and time. Summary tables will be prepared for each laboratory parameter. Figures of changes in laboratory parameters over time will be generated.

Results of vital sign assessments, ECGs, and physical examinations will be tabulated and summarized.

### 5.5.2 Demographics and Baseline Characteristics

Additional analyses will include summaries of subject demographics, baseline characteristics, compliance, and concurrent treatments. Concomitant medications will be coded and tabulated according to the WHO Drug Dictionary.

# 5.5.3 Study Treatment Administration and Compliance

Descriptive information will be provided regarding the number of acalabrutinib and pembrolizumab doses prescribed, the total number of doses taken, the number of days of treatment, and the number and timing of prescribed dose reductions and interruptions.

For each subject, acalabrutinib and pembrolizumab compliance will be described in terms of the relative dose intensity.

# 5.5.4 Analysis of Efficacy Parameters

#### **Response Rate**

The individual and composite endpoints of response and progression will be determined. Tumor control will be documented at each assessment by response category (see Section 4.2) as defined for each response parameter, date that response is first documented, and date of disease progression.

ORR will be defined as the proportion of subjects who achieve a response of PR or CR (see Section 4.2). For Part 3 subjects with MF, ORR will be defined as the proportion of subjects who achieve a response of clinical improvement or better (clinical improvement, PR, or CR) as shown in Table 9. ORR will be calculated and the corresponding exact 2-sided 90% and 95% CIs will be derived.

In addition, for subjects with CLL/SLL in Parts 1 and 2, a response will be assessed according to Table 6, which reflects modified International Working Group response criteria (Hallek 2008) as recently updated (Cheson 2012) to include PRL. For the purpose of this analysis, lymphocytosis at a given timepoint will be defined as absolute lymphocyte count which is above normal limits and is not ≥50% decreased from baseline.

For Part 3 subjects with MF, an additional analysis will evaluate response when defined as CR + PR only. A descriptive analysis will be done on the subgroups of subjects with MF who receive acalabrutinib alone or the combination of acalabrutinib and pembrolizumab.

#### **Duration of Response**

The duration of overall response defined as the interval from the first documentation of response to the earlier of the first documentation of definitive disease progression or death from any cause. Kaplan-Meier methods will be used to estimate event-free curves and corresponding quartiles (including the median). Data from surviving, non-progressing subjects

will be censored and detailed censoring rules will be specified in the statistical analysis plan (SAP).

#### Progression-free Survival

Progression-free survival is defined as the interval from the first dose date of acalabrutinib or pembrolizumab to the earlier of the first documentation of objective disease progression or death from any cause. Kaplan-Meier methods will be used to estimate the event-free curves and corresponding quartiles (including the median). Data from surviving, non-progressing subjects will be censored, and detailed censoring rules will be specified in the SAP.

#### Time-to-Next Treatment

Time-to-next treatment defined as the time from the first dose date of acalabrutinib or pembrolizumab to the start of the next treatment other than the study treatment. Kaplan-Meier methods will be used to estimate the event-free curves and corresponding quartiles (including the median). Data from subjects who have not received subsequent therapy will be censored at the earliest of death or the last time that lack of administration of a new therapy was objectively documented.

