9.6.4 Time to Next Treatment

Time-to-next treatment defined as the time from the first dose date of acalabrutinib or pembrolizumab to the start of the next treatment other than the study treatment. Descriptive statistics will be presented.

The summary of time to next treatment including the mean, minimum, maximum, median, Q1 and Q3 are provided for all the responders who have the next treatment for each disease group.

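### Time to next treatment: the protocol's Kaplan-Meier analysis censors deaths and the SAP's replacement leaves them out, so neither validly estimates how many subjects start a next therapy or when

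*Protocol*

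**What the plan says.** Protocol 5.5.4 (Time-to-Next Treatment) defines the endpoint as "the time from the first dose date of acalabrutinib or pembrolizumab to the start of the next treatment other than the study treatment". It calls for Kaplan-Meier curves and quartiles, including the median. Subjects without subsequent therapy are "censored at the earliest of death or the last time that lack of administration of a new therapy was objectively documented". Death is therefore neither an event nor a competing event.

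The neighbouring endpoints treat death differently. Progression-free survival runs from first dose "to the earlier of the first documentation of objective disease progression or death from any cause". Duration of response also ends at progression or death, and overall survival ends at death. For progression-free survival and duration of response the protocol leaves the detailed censoring rules to the SAP. For time to next treatment it states its own rule.

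The SAP takes another route. Section 9.6.4 says "Descriptive statistics will be presented", and its summaries "are provided for all the responders who have the next treatment for each disease group". Section 9.6.6 lists Kaplan-Meier for duration of response, progression-free survival and overall survival only. The censoring tables in Appendices 12.2 to 12.4 cover those same three endpoints. Section 10 nevertheless reports no major change from the protocol.

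**The concern.** Kaplan-Meier with a death censored assumes that the dead subject's later chance of starting a next therapy equals that of subjects still at risk. That chance is in fact zero. The estimate then answers a hypothetical question: how soon next treatment would start if nobody died first and deaths were independent of next treatment. The protocol does not say that this is the quantity it wants.

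Time to next treatment is one of the measures named in the secondary objective, and its value lies entirely in description. At stake is whether a reader can learn from it what proportion of each group went on to another therapy, and when. The protocol's rule gives a proportion that is too high. The SAP's replacement conditions on having responded and on having been treated again, so it gives no proportion at all.

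**Working it through.** **Figures in the documents.** Neither document gives a median, rate or event count for time to next treatment, so there is no plan figure to reproduce. The one mortality figure is in Protocol 1.4.2.1: 9 of 161 subjects with fatal adverse events, and 9/161 = 5.59%, which matches the stated 5.6%. It is a share of subjects, not of first events. Protocol 6.2.5 keeps deaths from disease progression out of serious adverse event reporting, so it need not include them. I use 5.6% only as a low-end anchor, not as a ceiling.

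**Assumptions (not in the documents).** Constant monthly hazards: λ for next treatment and δ for death without next treatment. The share of first events that are deaths is s = δ/(λ+δ).

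**Formulas.**

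- Kaplan-Meier with deaths censored: 1 − exp(−λt); median ln2/λ.
- Cumulative incidence of next treatment: [λ/(λ+δ)] × [1 − exp(−(λ+δ)t)]. It reaches 50% at −ln[1 − 0.5/(1−s)]/(λ+δ) when s is below 50%, and never otherwise.
- Next treatment or death: 1 − exp(−(λ+δ)t); median ln2/(λ+δ).

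**Numbers.** Set λ = ln2/12 = 0.0578, so Kaplan-Meier always gives a 12.0-month median and 75.0% at 24 months. For s = 20%, δ = 0.0578 × 0.2/0.8 = 0.0144 and λ+δ = 0.0722. Cumulative incidence at 24 months is 0.8 × (1 − exp(−1.733)) = 0.8 × 0.8232 = 65.9%, and 75.0 − 65.9 = 9.1 points. It reaches 50% at 0.981/0.0722 = 13.6 months. The composite median is 0.693/0.0722 = 9.6 months. The other rows follow in the same way:

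| Deaths as share of first events | Kaplan-Meier, 24 months | Cumulative incidence, 24 months | Overstatement (points) | Kaplan-Meier median (months) | Time to 50% cumulative incidence (months) | Median, next treatment or death (months) |
|---|---|---|---|---|---|---|
| 5.6% | 75.0% | 72.7% | 2 | 12.0 | 12.3 | 11.3 |
| 20% | 75.0% | 65.9% | 9 | 12.0 | 13.6 | 9.6 |
| 40% | 75.0% | 54.0% | 21 | 12.0 | 18.6 | 7.2 |
| 60% | 75.0% | 38.8% | 36 | 12.0 | never | 4.8 |

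The Kaplan-Meier columns do not move as deaths rise.

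**Simulation check.** I ran 1,000 replicates at n = 161 with administrative censoring uniform between 24 and 48 months. Kaplan-Meier gave 0.749 to 0.750 at 24 months. The Aalen-Johansen estimator gave 0.726, 0.657, 0.540 and 0.386 for the four rows. Results at n = 30 were close to these.

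**Other hazards.** Take λ = 0.10 and t = 12 months. One minus Kaplan-Meier is 1 − exp(−1.2) = 69.9%. Cumulative incidence is 63.6%, 55.6% and 45.5% for δ = 0.02, 0.05 and 0.10. At δ = 0.05 the Kaplan-Meier median is 0.693/0.10 = 6.9 months, cumulative incidence reaches 50% at ln4/0.15 = 9.2 months, and the composite median is 0.693/0.15 = 4.6 months. The pattern is the same.

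**The case against.** The strongest reply is that the SAP plans no Kaplan-Meier curve for this endpoint, so the protocol's bias may never reach a table. That is correct. A reader might infer that the report will contain an inflated curve, and the SAP as written does not support that. But the replacement conditions on two outcomes, response and next treatment, so it cannot recover the missing estimate. Because SAP section 10 declares no major change, it is also unclear which analysis governs.

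A reader might go further and infer that the bias will distort a comparison of aggressive with indolent histologies. The documents do not support that either. The layout by disease type comes from SAP 9.1 and 9.6.4, where this endpoint has no Kaplan-Meier. Protocol 5.1 says only that analyses will be by cancer type or overall, as appropriate. No comparison between histologies is planned, and SAP section 5 tests no formal hypothesis.

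It is also tempting to say that the Kaplan-Meier median simply exaggerates disease control. That holds only against the composite of next treatment or death. Against the cumulative incidence of next treatment, the same median is too early.

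Three further points stand. Defining the endpoint by treatment start alone is a legitimate choice, and the difference from progression-free survival is not in itself an error. The censoring rule is stated openly. Progression-free and overall survival, which count deaths, are reported alongside it.

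**Conclusion.** The point holds, with limits. The protocol's rule overstates the proportion who start a next therapy whenever deaths occur first, and the SAP's summary of treated responders does not replace it with a valid estimate.

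The size cannot be derived from the documents. It rests on constant hazards and an assumed 12-month Kaplan-Meier median: small (about 2 points at 24 months) if 5.6% of first events are deaths, and material from about 20% upward. Which end of that range applies depends on all-cause deaths without next treatment, which are not given.

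The endpoint is secondary and descriptive, the primary objective is safety, and the Part 2 activity criterion uses response rate. Severity is low to moderate.

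**What to change.** In SAP 9.6.4, estimate the cumulative incidence of next treatment with death before next treatment as a competing event (Aalen-Johansen), on the All-treated population by disease type. Censor only subjects alive without next therapy at their last documented contact. If a median is wanted, add a Kaplan-Meier analysis of next treatment or death, labelled as a composite. Add a matching rule to the SAP's censoring appendices.

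Align Protocol 5.5.4 at the next amendment, or record the departure in SAP section 10 in place of the statement that nothing major changed.

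No new data are needed: Protocol 4.4 and Appendix 5 already follow subjects for next treatment and survival about every 12 weeks. The method is standard. The costs are a small document change (an amendment goes to the ethics committee under Protocol 7.8) and less direct comparability with studies that censored deaths.

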#### **Overall Survival**

Overall survival is defined as the time from the first dose date of acalabrutinib or pembrolizumab until date of death due to any cause. Subjects who are known to be alive or whose survival status is unknown will be censored at the date last known to be alive. The analysis methods for overall survival will be similar to those described for progression-free survival.

## 5.5.5 PD or Biomarker Analyses

## 6.0 ASSESSMENT OF SAFETY

Safety assessments will consist of monitoring and recording AEs and SAEs; measurements of protocol-specified hematology, clinical chemistry (including thyroid function), urinalysis, and other laboratory variables; measurement of protocol-specified vital signs; and other protocol-specified tests that are deemed critical to the safety evaluation of the study drug(s).

## 6.1 **DEFINITIONS**

## 6.1.1 Adverse Events

An AE is any unfavorable and unintended sign, symptom, or disease temporally associated with the use of an investigational medicinal product (IMP), regardless of attribution.

This includes the following:

- AEs not previously observed in the subject that emerge during the protocol-specified AE reporting period, including signs or symptoms associated with the primary hematologic malignancy that were not present before the AE reporting period (see Section 6.2.1).
- Pre-existing medical conditions (other than the condition being studied) judged by the investigator to have worsened in severity or frequency or changed in character during the protocol-specified AE reporting period.
- Abnormal laboratory values considered clinically significant by the investigator should be reported as AEs.

The following are NOT considered an AE:

- **Pre-existing condition** that **has not worsened**: A pre-existing condition (documented on the medical history CRF) is not considered an AE unless the severity, frequency, or character of the event worsens during the study period.
- Preplanned hospitalization: A hospitalization planned before signing the ICF is not considered an SAE, but rather a therapeutic intervention. However, if during the preplanned hospitalization an event occurs, which prolongs the hospitalization or meets any other SAE criteria, the event will be considered an SAE. Surgeries or interventions that were under consideration, but not performed before signing the ICF, will not be considered serious if they are performed after signing the ICF for a condition that has not changed from its baseline level. Elective hospitalizations for social reasons, solely for the administration of chemotherapy, or due to long travel distances are also not SAEs.
- **Diagnostic testing and procedures**: Testing and procedures should not be reported as AEs or SAEs, but rather the cause for the test or procedure should be reported. If a test or procedure is done to rule out a diagnosis, the sign or symptom leading to the test/procedure should be the event term, and the event term should only be updated to the diagnosis if/when the diagnosis is confirmed. Testing and procedures performed solely as screening

measures (e.g., routine screening mammography or colonoscopy) should not be reported as AEs or SAEs.

- Abnormal laboratory results: Abnormal laboratory results are not AEs unless they are clinically significant. For example, a clinically significant laboratory result is one that requires treatment (for example, a blood transfusion for low hemoglobin) or requires a change in study drug (e.g., lowering the dose or withholding study drug while the laboratory finding resolves or stabilizes).
- **Progression of underlying malignancy**: Progression of underlying malignancy will not be reported as an AE if it is clearly consistent with the suspected progression of the underlying cancer. Hospitalization due solely to the progression of underlying malignancy should NOT be reported as an SAE. Clinical symptoms of progression may be reported as AEs if the symptoms cannot be determined as exclusively due to the progression of the underlying malignancy, or if they do not fit the expected pattern of progression for the disease under study.

Symptomatic deterioration may occur in some subjects. Symptomatic deterioration is when progression is evident in the subject's clinical symptoms and the investigator may elect not to perform further disease assessments.

If there is any uncertainty about an AE being due only to the disease under study, it should be reported as an AE or SAE.

